10. APPENDICES

Appendix 1. Statistical Methodology Details

Appendix 1.1. Finkelstein-Schoenfeld Example Scoring Algorithm

Scenario	i/j	All-cause Mortality	Survival Time (from baseline)	Cardiovascular-related hospitalization	Score
1	i	Dead	-	-	-1
	j	Alive	-	-	
2	i	Dead	Low	-	-1
	j	Dead	High	-	
3	i	Dead	Tied	High	-1
	j	Dead	Tied	Low	
4	i	Dead	Tied	Tied	0
	j	Dead	Tied	Tied	
5	i	Alive	-	High	-1
	j	Alive	-	Low	
6	i	Alive	-	Tied	0
	j	Alive	-	Tied	

Subjects that are tied on “all-cause mortality” will be compared by frequency of cardiovascular-related hospitalization. If the 2 subjects have different follow-up times, the smaller of the 2 follow-up times will be used in comparing the frequency of cardiovascular-related hospitalization.

If i and j are reversed in severity than the value assigned to i is +1.

Appendix 1.2. Definition and Use of Visit Windows in Reporting

The following describes the clinical visits windows allowed within the protocol after month 1 visit:

Clinic Visits (Months 3, 6, 9, 12, 15, 18, 21, 24, 27, 30) ± 2 weeks

End of Study Visit (Month 30) ± 2 weeks or Early Study Discontinuation

However, in order to maximize the use of all available data, the visit windows for each visit are expanded as follows:

For endpoints collected every 3 months:

Clinic Visits (Months 3, 6, 9, 12, 15, 18, 21, 24, 27, 30) ± 6 weeks

All nominal visits (months 3, 6, 9, 12, 15, 18, 21, 24, 27, 30) will use the data as collected from that visit. Early termination visits will never replace an existing visit. If the visit covered by the windowing rules above is already populated with an existing nominal visit, then the early termination visit should be mapped forward to the next 3 month visit.

For endpoints collected every 6 months:

Clinic Visits (Months 6, 12, 18, 24, 30) ± 3 months

All nominal visits (months 6, 12, 18, 24, 30) will use the data as collected from that visit. Early termination visits will never replace an existing visit. If the visit covered by the windowing rules above is already populated with an existing nominal visit, then the early termination visit should be mapped forward to the next 6 month visit.

For Echocardiogram collected at months 6, 18, and 30:

Clinic Visits (Months 6, 18, 30) ± 6 months

All nominal visits (months 6, 18, 30) will use the data as collected from that visit. Early termination visits will never replace an existing visit. If the visit covered by the windowing rules above is already populated with an existing nominal visit, then the early termination visit should be mapped forward to the next nominal visit.

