| Brief physical examination | | X | | X | X | X | X | X | X | X | X | X | X | X | |
| Height | X | | | | | | | | | | | | | | |
| Weight | X | X | | X | X | X | X | X | X | X | X | X | X | X | X |
| 12 Lead ECG | X | X ^b | | X | | X | | X | | X | | X | | | X |
| Vital signsc | X | X | | X | X | X | X | X | X | X | X | X | X | X | X |
| Echocardiogram | X | | | | | X | | | | X | | | | | X |
| Tissue biopsy ^d | X | | | | | | | | | | | | | | |
| Laboratory samples | | | | | | | | | | | | | | | |

| Protocol Activity | Screening Period | Base Line | | Month | | | | | | | | | | |
|---|------------------|-----------|-------------------------------------|--------------------|-------|---------------------|---|---|---|---|----|----|----|----|
| | | | | Day -45 to Day -10 | Day 1 | Week 2 ^a | 1 | 3 | 6 | 9 | 12 | 15 | 18 | 21 |
| Hematology | X | X | X | X | | X | | X | | X | | X | | X |
| Serum Chemistry | X | X | X | X | X | X | X | X | X | X | X | X | X | X |
| Coagulation (INR, PT – Local) ^c | X | X | | X | | X | | X | | X | | X | | X |
| Retinol Binding Protein | | X | | X | | X | | X | | X | | X | | X |
| Serology (HBsAg, anti-HCV, and HIV) | X | | | | | | | | | | | | | |
| Serum/urine test for primary (light chain) amyloidosis (AL) | X | | | | | | | | | | | | | |
| Urinalysis | X | X | | X | | X | | X | | X | | X | | X |
| Genotyping | X | | | | | | | | | | | | | |
| Pregnancy test ^f | X | X | | X | | X | | X | | X | | X | | X |
| TTR stabilization, TTR oligomer concentration, and TTR concentration ^g | | X | | X | | X | | X | | X | | X | | X |
| Urine TTR oligomer concentration ^h | | | | | | | | X | | X | | X | | X |
| Tafamidis Concentrations ⁱ | | X | | X | | X | | X | | X | | X | | X |
| Tafamidis concentrations (for subjects receiving dialysis or hemofiltration) ^j | | | -----Any time during the study----- | | | | | | | | | | | |
| Diflunisal concentration ^k | X | X | | X | | X | | | | X | | | | X |
| Pharmacogenetic sample | | X | | | | | | | | | | | | |
| NT – proBNP, troponin I | X | X | | | | | | X | | | | | | X |
| 6MWT | X | X | | | | X | | X | | X | | X | | X |
| KCCQ ^l | | X | | | | X | | X | | X | | X | | X |
| EQ-5D-3L ^m | | X | | | | X | | X | | X | | X | | X |
| PGA ⁿ | | X | | | | X | | X | | X | | X | | X |
| NYHA classification ^o | X | X | | | | X | | X | | X | | X | | X |

| Protocol Activity | Screening Period | Base Line | Month | | | | | | | | | | | |

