2.1. Study Design

This is a Phase 3, multicenter, international, three-arm, parallel design, placebo-controlled, randomized study with a 30-month double-blind treatment phase, to determine efficacy, safety and tolerability of tafamidis on clinical outcomes in subjects with either transthyretin genetic variants or wild-type transthyretin resulting in amyloid cardiomyopathy (TTR-CM).

There will be approximately 400 subjects enrolled in the study in a 2:1:2 ratio (placebo:20 mg:80 mg). The subjects will be allocated to the 3 arms of the study in the following manner: n=160 in the placebo arm, n=80 in the 20 mg arm, and n=160 in the 80 mg arm. Subjects who experience adverse events that may be associated with poor tolerability to treatment with tafamidis that may impact dosing adherence have the option of blinded treatment re-assignment and potential dose-reduction (see [Section 5.5 of protocol](#)). Subjects will be stratified during enrollment by TTR genotype (variant and wild-type) and structured such that greater than 30% of randomized subjects have a TTR mutation and greater than 30% of subjects have a diagnosis of wild-type TTR cardiomyopathy, with the intent to enroll comparable numbers between the variant and wild-type groups.

Enrollment may be closed for either wild-type or variant stratum in order to enroll at least 30% of subjects with each TTR genotype (wild-type and variant).

Additionally, stratification to treatment assignment will be done for Baseline severity of disease based on NYHA classification (NYHA Class I and NYHA Classes II and III combined). Stratification will be implemented in order to maintain a balance of both TTR genotype and disease severity across the treatment assignments. The site will ensure a Month 30 follow-up contact to determine the subject's vital status and whether the subject has had a heart and / or liver transplant or implantation of cardiac mechanical assist device. Upon completion of the study at the Month 30 visit, subjects may be eligible for treatment with tafamidis in a separate study (B3461045), which will permit the collection of additional safety and efficacy data, and may include the assessment of hospitalizations, mortality, and other outcomes relating to disease progression. For the purpose of this study, 30 months is defined as 910 days. Eligibility for the extension study (B3461045) requires subject participation in this study at least through Day 896 (Month 30 minus 2 weeks).

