- All-cause mortality and frequency of all-cause hospitalizations,
- All-cause mortality and cardiovascular-related days hospitalized using the Finkelstein-Schoenfeld analysis,
- Cardiovascular-related mortality and frequency of cardiovascular-related hospitalization using the Finkelstein-Schoenfeld analysis.

The exploratory endpoints listed below will be evaluated at each time point post-baseline using a mixed model repeated measures ANCOVA (MMRM) as detailed in [Section 8.1.3](#).

- Change from Baseline in Kansas City Cardiomyopathy Questionnaire: (KCCQ) domain scores (Physical limitation, Symptom stability, Symptom frequency, Symptom burden, Total symptom, Self-efficacy, Social limitation, and Quality of life) and clinical summary score,
- Change from Baseline in EuroQoL-5 Dimensions (EQ-5D-3L) Index Score and visual analog scale (VAS) scores,
- Patient Global Assessment,
- Change from Baseline in Modified Body Mass Index,

- Change from Baseline in NT-proBNP concentration,
- TTR oligomer concentration at each time point,
- TTR concentration at each time point,
- Change from Baseline in echocardiographic parameters:
 - End-diastolic interventricular septal wall thickness (mm),
 - Left ventricle posterior wall thickness (mm),
 - Left ventricular ejection fraction (%),
 - Left ventricular stroke volume (mL),
 - Global longitudinal strain,
 - Circumferential strain mid global,
 - Radial strain mid global.

All other echocardiographic parameters listed as endpoints in [Section 6.1.4](#) will be analyzed descriptively.

The TTR oligomer concentration and TTR concentration will additionally be analyzed by dose. Descriptive statistics are presented by visit for the NYHA Classification (Class I, II, III, and IV). The number and percent of subjects with an improvement (decrease by at least one classification), those who worsened (increase by at least one classification), and those with no change (same classification) from baseline are presented at each visit using a shift table. A cross-tabulation of baseline severity level and post baseline change level will be presented at each visit for Patient Global Assessment scale.

Plasma concentrations of tafamidis will be summarized with descriptive statistics (n, arithmetic mean, standard deviation, coefficient of variation, geometric mean, median, and minimum and maximum) by dose, visit, and nominal time.

Plasma concentrations of diflunisal will be provided as listings by visit.

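### The three-monthly visit windows in SAP Appendix 1.2 leave a six-day gap between every pair of visits, and NT-proBNP fits none of the window rules

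*SAP*

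**What the plan says.** SAP Appendix 1.2 starts from the protocol's visit windows and then says that "in order to maximize the use of all available data, the visit windows for each visit are expanded as follows". Three rules follow:

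- Three-monthly endpoints: "Clinic Visits (Months 3, 6, 9, 12, 15, 18, 21, 24, 27, 30) ± 6 weeks".
- Six-monthly endpoints: "Clinic Visits (Months 6, 12, 18, 24, 30) ± 3 months".
- Echocardiography: ±6 months around Months 6, 18 and 30.

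Under every rule a nominal visit keeps its own data, so the windows decide only where an early-termination value goes. A value moves on to the next visit under one condition: "If the visit covered by the windowing rules above is already populated with an existing nominal visit".

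On the length of the schedule, SAP Section 2.1 says: "For the purpose of this study, 30 months is defined as 910 days".

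The row "NT – proBNP, troponin I" in the protocol's Schedule of Activities, with Protocol Sections 6.2.7 and 6.2.13, places the post-baseline samples at Month 12 and at Month 30 or early discontinuation. SAP Section 8.2.4 lists "Change from Baseline in NT-proBNP concentration" among the endpoints to be analysed by MMRM at each post-baseline time point.

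**The concern.** The appendix aims to use all available data, yet the three-monthly rule is narrower than the spacing of the visits it serves. The other two rules run from midpoint to midpoint, so this one looks like an oversight. A value from an early-termination visit that falls between two windows is assigned to no visit. It cannot move forward either, because that rule presupposes a window that already covers the date.

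NT-proBNP raises a related question. Its schedule is not three-monthly, not six-monthly and not that of the echocardiogram, so the SAP gives no rule for its early-termination values although they would enter a by-visit model. SAP Amendment 4 gave echocardiography a window built on its own collection visits, but did not do the same for NT-proBNP.

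At stake are a few exploratory and safety values, and a choice about dropout data that would otherwise be left to programming.

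**Working it through.** **Inputs.** 30 months = 910 days (SAP Section 2.1). Window half-width = 6 weeks = 42 days (Appendix 1.2). Protocol Section 6 schedules intermediate visits by calendar date and Month 30 at 910 days, so both a 91-day grid and calendar months are shown.

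**The plan's own day count.** Month 30 minus 2 weeks = 910 − 14 = Day 896, as SAP Section 2.1 states. Ten three-monthly intervals give 910/10 = 91 days = 13.0 weeks.

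**Gap per interval, 91-day grid.** A window spans 2 × 42 + 1 = 85 days counting both ends. Gap = 91 − 85 = 6 days, and 6/91 = 6.6%. In elapsed time the window is 84 days, and the gap is 7/91 = 7.7%.

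**Total.** There are nine gaps between Month 3 and Month 30: Days 134–139, 225–230, 316–321, 407–412, 498–503, 589–594, 680–685, 771–776 and 862–867. That is 9 × 6 = 54 days. The Month 3 window opens on Day 91 − 42 = 49, so the span to Day 910 is 862 days, and 54/862 = 6.3%.

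**Calendar months.** The interval is 3 × 365.25/12 = 91.31 days. With unrounded target dates, 66 of 861 days are uncovered (7.7%). Rounding targets to whole days gives 57 of 865 (6.6%). The range is therefore 6.3% to 7.7%.

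**Does the forward rule help?** No. Day 136, for example, is 45 days after Day 91 and 46 days before Day 182. No window contains it, so the condition for moving forward is not met.

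**What is reached.** Serum chemistry is taken at every study visit (Protocol Section 7.6.6), and weight at every clinic visit. mBMI is BMI times albumin (Protocol Section 7.4), so it is available every three months. I take it to be windowed that way, since the SAP does not name its rule. mBMI is an exploratory MMRM endpoint. Chemistry gets descriptive summaries of change (SAP Section 8.2.5).

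**After the change.** On the 91-day grid, midpoints give ±45.5 days, and 0 of 862 days are uncovered. With calendar targets and Month 30 at Day 910, a fixed ±45.5 days would still leave 2 days uncovered and put Days 865–867 in two windows. Assigning to the nearest target date avoids both problems.

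**NT-proBNP, if the six-monthly rule were applied.** Assume exits spread evenly over 30 months, and Month 12 filled for anyone leaving later.

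| Exit month | Filed at | Share of exits |
|---|---|---|
| 0–3 | no window | 3/30 = 10% |
| 3–9 | Month 6 | 6/30 = 20% |
| 9–12 | Month 12 | 3/30 = 10% |
| 12–21 | Month 18 (12–15 moved forward) | 9/30 = 30% |
| 21–27 | Month 24 | 6/30 = 20% |
| 27–30 | Month 30 | 3/30 = 10% |

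Months 6, 18 and 24 have no scheduled sample and would receive 20 + 30 + 20 = 70% of exit values, or 21/27 = 77.8% of those from Month 3 on. From Month 3 on, the three-monthly rule would send 81.8% to unscheduled months and the echocardiogram rule 77.8%.

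**The case against.** The strongest answer is that very little depends on the gap. Nominal visits keep their own data, so only early-termination values can fall into it. The primary analysis uses no visit windows. The six-minute walk and KCCQ are six-monthly, with windows contiguous from Month 3. Vital signs are specified as listings by subject. That leaves one modelled exploratory endpoint and descriptive chemistry. All of this stands, and it sets the weight of the point.

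The fix also does not reach every value. Midpoint windows begin about Day 46, and a six-monthly endpoint measured at an exit before Month 3 still has no window. That is a separate matter at the start of the schedule.

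Stronger readings are tempting, but the documents do not support them:

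- **A reader might infer that NT-proBNP values will be filed at Months 6, 18 and 24.** The SAP never assigns NT-proBNP to the six-monthly rule. It states no rule, so the table above is conditional.
- **A reader might infer that the MMRM will report contrasts among dropouts only, with a covariance matrix that cannot be estimated.** Under the six-monthly rule, one subject could supply only 3 of the 10 visit pairs (12–18, 12–24, 12–30). But that rule is not assigned, and SAP Section 8.1.3 allows a structure other than unstructured where appropriate.
- **A reader might infer that the lost values come from the sickest subjects.** Protocol Section 6.3 gives several reasons for withdrawal, including the subject's own request and inability to keep visits. It does not describe those who attend an early-discontinuation visit as sicker.

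**Conclusion.** The gap is real and follows from the SAP's own day count: six days between each pair of three-monthly windows, 6.3% of the time from Day 49 to Day 910 and up to 7.7% on calendar months. It works against the stated purpose of the expanded windows, and no other rule in the appendix covers it. The percentage equals the share of early terminations affected only if these are evenly spread over time, which is an assumption. The consequence is minor and confined to exploratory mBMI, if that is windowed three-monthly, and by-visit chemistry summaries.

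The NT-proBNP point is secondary. What the documents establish is that a modelled endpoint fits none of the three window rules. Whichever of those rules were borrowed, most early-termination values from Month 3 on would carry the label of a month with no scheduled sample. They do not establish that this will be done.

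**What to change.** In SAP Appendix 1.2, replace ±6 weeks with contiguous midpoint windows: assign an early-termination value to the nearest target date, which is ±6.5 weeks on the 91-day schedule. State whether targets are counted in 91-day steps or calendar months, and add a tie rule for shared boundaries. The same tie rule can serve the six-monthly windows, where Months 9, 15, 21 and 27 each lie in two windows.

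Add an NT-proBNP rule on the echocardiogram pattern: visits 12 and 30 only, ±9 months, midpoint Month 21, moving forward to Month 30 if Month 12 is already filled. Fit its model with those two visits. With evenly spread exits (an assumption), Month 12 takes exits from Months 3–12 (9/30 = 30%) and Month 30 takes those from Months 12–30 (60%). About 10%, before Month 3, stay unassigned.

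The cost is a few lines of text and programming before unblinding. The forward rule has a price: a value drawn soon after Month 12 would be labelled Month 30, up to 18 months late. If the sponsor prefers to list values from Months 12–21 instead of modelling them, the SAP should say that, under even exits, this excludes about 9/30 = 30% of exit values in addition to the 10% before Month 3, leaving 60% modelled.

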6.2.13. Month 30 Visit or Early Study Discontinuation

Subjects will take their scheduled dose at home on the day of the clinic visit and record the actual times of dosing for the 2 doses prior to the visit on their Subject Daily Dosing Diary. Study site personnel will record in the CRF the time of dosing the time of dosing the day before and the day of the Month 30 visit as recorded by the subject on their Subject Daily Dosing Diary. The following procedures will be performed for all subjects at the Month 30 visit or at the time of Early Study Discontinuation:

1. Full physical examination with weight.
2. Single 12-Lead ECG.
3. Vital signs (systolic and diastolic blood pressure supine and standing, pulse rate supine and standing, respiration rate, and body temperature).
4. Echocardiogram.
5. Blood and urine sample collection for the following clinical laboratories:
 - a. Hematology;

- b. Serum Chemistry;
 - c. Coagulation (INR, PT);
 - d. Retinol Binding Protein;
 - e. Urinalysis;
 - f. Urine pregnancy test – for women of childbearing potential.
6. Collect blood sample for TTR stabilization, TTR oligomer concentration, and TTR concentration assays at any time during the clinic visit.
 7. Collect blood sample for tafamidis concentration at any time after dosing and record the actual time of the blood sample as well as the time of drug dosing from the subject's Subject Daily Dosing Diary.
 8. At selected centers only, collect urine sample for assay development of TTR oligomer concentration.
 9. Collect blood sample for NT-proBNP and troponin I.
 10. Collect blood sample for diflunisal concentration ([Section 7.7.3](#)).
 11. 6-Minute Walk Test ([Appendix 4](#)).
 12. Kansas City Cardiomyopathy Questionnaire ([Appendix 1.1](#)).
 13. EQ-5D-3L ([Appendix 2](#)).
 14. Patient Global Assessment ([Appendix 3](#)).
 15. NYHA classification.
 16. Documentation of concomitant medications.
 17. Record dosing adherence.
 18. Adverse event reporting.
 19. Hospitalization determination.
 20. Documentation of vital status, transplant or cardiac mechanical assist device status (within 2 weeks of the target Month 30 visit).

Additionally, except for subjects who are randomized into the extension study (Study B3461045), subjects will have a 4-week (28 calendar days) safety follow-up visit after the last dose of the study medication for collection of adverse events. This visit can be completed by telephone.

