7.7.3. Diflunisal Concentration

After the recording of ECGs, Echocardiograms and blood pressure, a blood sample will be collected to determine if the subject has taken diflunisal. The blood sample for this assessment will be taken at Screening, Baseline and Months 1, 6, 18, and 30. Use of diflunisal during the study is not permitted. Subjects taking diflunisal will be appropriately counselled. Such subjects will be handled as protocol violators in the analysis as described in the Statistical Analysis Plan.

Samples will be analyzed using a validated analytical method in compliance with Pfizer standard operating procedures.

Detailed instructions for collection, storage, labeling, and shipment of all samples are provided in a separate study laboratory manual.

7.7.4. 6-Minute Walk Test (6MWT)

A 6MWT will be conducted during the Screening period and at the Baseline visit and at Month 6, 12, 18, 24, and 30 visits (or Early Study Discontinuation). There will be one 6MWT during the Screening period. Subjects who are unable to walk 100 meters at Screening will be considered a Screen Failure.

The test will be conducted in accordance with guidelines established by the American Thoracic Society.

Detailed instructions for conducting the 6MWT are provided in [Section Appendix 4](#).

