1. AMENDMENTS FROM PREVIOUS VERSION(S)

- **Status of study when amendment made:**

Study is ongoing and remains blinded.

- **Details of Changes and Rationale:**

Amendment 1 (SAP Version 2)

Section of the SAP	Summary of change	Rationale
Various sections	Typographical corrections and clarifications For example: Changed “patients” to “subjects” for consistency.	Corrected minor typographical errors and inconsistent terminology.
2.1 Study Design	
 • Clarified specification of sample size as 400 subjects. • Specified the duration of 30 months to be equal to 910 days. 	Inserted new text from protocol amendment 1.
5.6.2. Deviations Assessed Post Randomization	Added use of 3 prohibited medications, ie, diflunisal, tauroursodeoxycholate, and doxycycline as criteria for exclusion from Per-Protocol Analysis Set.	Use of prohibited medication as described in protocol amendment 1 Section 5.8.1. Contraindicated Therapies.
6.1.4. Exploratory Endpoints	Added echo strain and other parameters.	Inserted new text from protocol amendment 1.
8.1.1. Finkelstein Schoenfeld Analyses	
 • Clarified text around algorithm involving “censored” subjects. • Removed sentence related to analysis of “indeterminate” events. 	
 • Modified text to improve clarity. • Removed sentence regarding analysis of events adjudicated as “indeterminate” as it was inconsistent with the last sentence of the first paragraph of Section 8.1.1.
8.2.2. Key Secondary Analyses	Added specification of pattern mixture analysis as a supplemental analysis of the key-secondary analyses.	Inserted new text per agreement with FDA.
8.2.3. Secondary Analyses	Added a statement describing the handling of deaths adjudicated as “indeterminate” similar to the handling of “hospitalizations”.	Added missing detail for handling “indeterminate” deaths in the analysis.
8.2.4. Exploratory Analyses	
 • Added analysis of placebo vs 80 mg randomized subjects who were not downtitrated as requested by PMDA. • Added analysis by region as requested by FDA. • Added additional exploratory endpoints. 	
 • Added analysis requested by PMDA and FDA. • Added exploratory endpoints to be consistent with protocol amendment 1.

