Section 8.1.1, Section 6.4	Clarification of how subjects incorrectly classified during randomization will be handled in the primary analysis.	Subjects who were incorrectly classified during randomization will be analyzed using the correct value of the stratification factors (TTR Genotype or NYHA baseline classification) in the primary analysis.
Section 8.2	Frequency of TTR mutation analysis added.	Frequency of various TTR mutations enrolled in the study will be summarized.
Section 8.2.1, Section 8.2.4	Clarified the term “down-titration” to “dose reduction”.	Wording modified per protocol to more accurately represent the change in dose that may occur when a subject is unable to tolerate the randomized dose.
Section 8.2.4	Cross-tabulation summary added for Patient Global Assessment.	Additional descriptive summary for Patient Global Assessment added.
Section 8.2.5	A lag of 28 days will be used in determining treatment-emergence.	Clarifying and documenting a program wide standard procedure with respect to lag.
Appendix 1.2	Visit window algorithm details added.	An algorithm was added to detail how early termination visits will be assigned to nominal study visits.

Amendment 4 (SAP Version 5)

Section of the SAP	Summary of change	Rationale
6.1.4. Exploratory Endpoints	Updated KCCQ related domain and summary scores.	Updated to be consistent with the developers’ names for the KCCQ domain and summary scores.
8.1.1. Finkelstein Schoenfeld Analyses	Corrected an error in the notation (replace subscript “i” with “j”) describing the calculation of U_i .	Update to correct a minor error in the equation describing calculation of U_i ($U_i = \sum_{j \in A_k} u_{ij}$)
8.2.2. Key Secondary Analyses	Updated reference for sample SAS code for pattern mixture analysis from Appendix 1.2 to Appendix 1.3 .	Updated to correct the referenced Appendix number.
8.2.4. Exploratory Analyses	Removed exploratory analysis comparing subjects reduced to 40 mg vs placebo.	The analysis is not meaningful given the very low number of total blinded dose reductions in the study.
8.2.4. Exploratory Analyses	Added tables summarizing plasma concentrations of tafamidis and a listing of plasma concentration of diflunisal.	Added plasma based summary tables for tafamidis and listing for diflunisal.

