Appendix 1.3. Sample SAS Code for Analyses Described in Sections 8.1.2 – 8.2.6

Sample SAS code to fit the mixed model repeated measures specified in [Section 8.1.3](#) is given below. The response variable Y is the change from baseline at the study visits.

```
PROC MIXED DATA=xxx METHOD=REML EMPIRICAL;  
CLASS pid center trt visit genotype;  
MODEL y= ybase trt visit genotype trt *visit;  
RANDOM int/SUBJECT=center;  
  
REPEATED visit /SUBJECT= pid (center) r type=UN;  
  
RUN;
```

Sample SAS code for the survival analysis specified in [Section 8.1.2](#) is given below.

```
PROC LIFETEST DATA=xxx PLOTS=(s) graphics;  
TIME dur *status(0);  
STRATA trt;  
RUN;  
  
PROC PHREG DATA=xxx;  
MODEL dur*status(0)=trt genotype NYHAbase/ ties=EXACT;  
RUN
```

Sample SAS code for the ANOVA specified in [Section 8.1.4](#) is given below.

```
PROC GLM DATA=xxx;  
CLASS trt genotype NYHAbase;  
MODEL y= trt genotype NYHAbase trt*genotype trt*NYHAbase;  
RUN;
```

Sample SAS code for the Poisson regression specified in [Section 8.1.5](#) is given below.

```
PROC DATA=xxx;  
ln_styyr=log(styyr);* log transformation to normalize duration of participation ;  
RUN;  
  
PROC GENMOD DATA=xxx;  
CLASS trt genotype NYHAbase;  
MODEL y= trt genotype NYHAbase trt*genotype  
trt*NYHAbase/ type 3 dist=poisson link=log offset=ln_styyr;  
RUN;
```

Sample SAS code for the CMH test specified in [Section 8.1.6](#) is given below. In the code below, the variable NYHA_GENOTYPE is obtained from combining NYHA baseline classification and TTR genotype into one variable (with 4 levels).

```
PROC FREQ DATA=xx;
TABLES NYHA_GENOTYPE*TRT*STABILIZED / CMH
RUN;
```

Sample SAS code for the pattern mixture analysis specified in [Section 8.1.5](#) is given below.

```
PROC MIXED DATA=xxx empirical;
CLASS pid visit center trt pattern genotype;
MODEL y= ybase visit trt genotype pattern visit*trt
trt*pattern / solution;
random int/subject=center;
repeated visit /subject= pid (center) r type=UN;
ESTIMATE 'Tafamidis vs placebo Month 30'
trt 1 -1 visit*trt 0 0 0 0 0 0 0 1 -1
trt*pattern 0.5 0.5 -0.5 -0.5 /cl e; * Placebo adjusted LSMEANS of Tafamidis
averaged over the pattern (equal weight=0.5);
run;
```

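### Does analysing some early-termination 6MWT and KCCQ values as Month 30, three to six months early, call for a change to the key secondary analyses?

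*SAP*

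**What the plan says.** The 6MWT and KCCQ are scheduled at Months 6, 12, 18, 24 and 30 and are also taken when a subject leaves early. Protocol Section 6.2.13, which lists both, opens: "The following procedures will be performed for all subjects at the Month 30 visit or at the time of Early Study Discontinuation".

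SAP Appendix 1.2 widens the analysis windows "in order to maximize the use of all available data". For these endpoints the window is "Clinic Visits (Months 6, 12, 18, 24, 30) ± 3 months". An early-termination value never overwrites an attended visit. If the visit whose window contains it is already filled, "then the early termination visit should be mapped forward to the next 6 month visit". The log for Amendment 3 in SAP Section 1 records the step as deliberate: "An algorithm was added to detail how early termination visits will be assigned to nominal study visits". The same section gives the status at amendment: "Study is ongoing and remains blinded".

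The key secondary tests in SAP Section 8.2.2 are Month 30 contrasts from a repeated-measures model, with 6MWT first and KCCQ second. Visit is categorical in the sample code ("CLASS pid center trt visit genotype"), so a value counts at its assigned visit and its actual date does not enter. Two pattern-mixture analyses group subjects by whether they have Month 30 data (Case 1) or data around Month 15 or later (Case 2). Neither definition says whether the assigned visit or the calendar date decides.

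**The concern.** The Month 30 window opens at Month 27, yet the forward step can put a value from Month 24.5 under the Month 30 label. In a progressive disease a value taken several months early misses some decline. If placebo subjects decline faster, such values would tend to narrow the treatment difference at the time point on which 6MWT is tested, and KCCQ can be declared significant only if 6MWT succeeds.

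The planned checks do not clearly cover this. The per-protocol criteria in SAP Section 5.6.2 do not name these values, and the pattern-mixture model retains them. The pattern definitions add a reproducibility worry, since two programmers could place the same subject in different patterns.

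**Working it through.** The plan gives no figure to reproduce. The check is to apply the rule and then size its effect.

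**1. What the rule does** (all earlier scheduled visits attended)

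| Exit at month | Window it falls in | Label given | Months early |
|---|---|---|---|
| 12.5 | Month 12 (9–15), filled | Month 18 | 5.5 |
| 24.5 | Month 24 (21–27), filled | Month 30 | 5.5 |
| 26.75 | Month 24 (21–27), filled | Month 30 | 3.25 |
| 28 | Month 30 (27–33), empty | Month 30 | 2 |

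Only exits after an attended Month 24 visit and before Month 27 reach Month 30 from outside its window. They are 3 to 6 months early, or up to about 6.5 if Month 24 was attended two weeks early.

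**2. Metres per value.** Protocol Section 1.2.1 reports 12-month 6MWT changes of −44 m (untreated cohort) and −11 m (open-label tafamidis). Assume linear decline and an average of 4.5 months early:

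- placebo: 44/12 × 4.5 = 16.5 m missed
- tafamidis: 11/12 × 4.5 = 4.1 m missed
- difference: 12.4 m

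**3. Shift in the Month 30 difference.** Assume 2%, 5% or 10% of subjects leave alive, with a completed test, evenly over Months 24–30. Half of them are affected: 1.6/2.4, 4/6 or 8/12 values (placebo/tafamidis).

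- Over all 160/240 subjects: 12.375 × 0.01, 0.025 or 0.05 = 0.12, 0.31 or 0.62 m.
- Over those left after the deaths assumed in Protocol Section 9.1 (160 × 0.75 = 120; 240 × 0.875 = 210), the 10% case is 8/120 × 16.5 − 12/210 × 4.125 = 1.10 − 0.24 = 0.86 m. The 2% and 5% cases give 0.17 and 0.43 m.
- A deliberately lopsided extreme has 10% of placebo Month 30 values mapped, all six months early, and none on tafamidis: 0.10 × 44/12 × 6 = 2.2 m.

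**4. Against the noise.** A simulated unstructured repeated-measures model (five visits, 160:240, slope SD 2 m/month and residual SD 35 m, both assumed; no centre or genotype terms) gives a standard error near 7.6 m.

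- Step 3 range: 0.12/7.6 = 0.02 to 0.86/7.6 = 0.11 standard errors.
- Lopsided extreme: 2.2/7.6 = 0.29.
- If the true standard error were half as large, 0.11 would become about 0.23.

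In the same simulation with 10% exits, excluding the mapped values changes the estimate by +0.59 m if subjects do not deteriorate before leaving. The change is −0.81 m if they drop by 40 m on placebo and 10 m on tafamidis before leaving. The sign turns when the mean pre-exit drops differ by about the 12.4 m of step 2.

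**5. Pattern definitions.** Further assume 10% of subjects leave before Month 24. Using dates instead of labels then moves about 3, 9 or 17 subjects from Pattern 1A to 1B, and about 5 from 2A to 2B. The mean change in the equal-weight estimate is about 0.1 m at most. Within a single trial its SD is 0.5–1.1 m in Case 1 (standard error 8.1 m) and 1.6–1.9 m in Case 2 (standard error 9.1 m), so at most 1.9/9.1 = 0.21 standard errors.

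**The case for a change.** The best argument for a change is that prespecifying a rule does not show the result is robust to it. The 6MWT test stands ahead of KCCQ, visit is categorical so timing is invisible to the model, and the per-protocol and pattern-mixture repeats do not promise to remove these values. One sensitivity model per endpoint, a count by arm and one clarifying sentence would cost little.

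The description of the gap stands, with one qualification. The deviation list in SAP Section 5.6.2 is open-ended and is reviewed before unblinding, so removal from the per-protocol set is possible, though not promised.

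The case for acting is weaker. The extra run would leave the main analysis untouched, and step 4 already indicates that it would not alter the conclusion. Removing the values from the main model would be a trade: an observed late measurement, perhaps showing real deterioration before exit, would give way to extrapolation from Month 24.

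Defining patterns by actual date does not settle matters by itself. A Month 28 exit has Month 30 data under a three-month window but not under the Protocol's two-week window. A subject could also be classed as lacking Month 30 data while still contributing a Month 30 row to the same model. SAP Section 1 records the pattern-mixture analysis as added by agreement with the FDA, so redefining it is more than an edit.

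Case 1 reads naturally through Appendix 1.2, which decides which visit a value belongs to. Case 2 is the one part really open, because neither endpoint is scheduled at Month 15.

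**Conclusion.** No change to the plan is needed. Some values are analysed three to six months early, but this is the second step of one explicit algorithm, fixed while blinded for a stated reason, and not a departure from it. The likely shift in the Month 30 6MWT difference is about 0.1 to 0.9 m, up to about 0.11 standard errors, in an uncertain direction. Even the lopsided extreme of 2.2 m is under a third of a standard error.

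These figures rest on linear extension of 12-month changes from two unmatched cohorts, on exit rates the documents do not give, and on a single assumed pair of SDs. The 10% case is a high assumption and not a bound: the Day 896 condition for entering the extension study (Protocol Section 3) encourages subjects to stay but does not cap exits. No KCCQ figure can be derived from the documents.

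The label-or-date question is missing detail that the analysis programmers can settle in their specifications before unblinding, most simply by using the Appendix 1.2 visit label throughout. Counting the mapped values by arm, or running the model once without them, is a reasonable option for the study report but not a correction that the plan requires.
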